2.3 Pelvic function daily diaries

To look for off-target or carry-over stimulation effects, participants will be asked to complete a daily bladder, bowel, and sexual function diary from two days before until two days after a session, to provide objective measures across several parameters (e.g. incontinence episodes, regularity). The full diary is in section 44.1. Figure 3 shows the daily questions. Surveys will be completed in REDCap or over the phone. Spinal cord injured patients will also have a question asking if they had an autonomic dysreflexia event.

2.4 Patient timeline

Research Activity timetable summary:

1. Consent
2. Pre-session surveys

3. Study visit 1:

- Days 1 & 2: At-home diary
- Day 3: Test session and diary
- Days 4 & 5: At-home diary

4. Interval of one to five months

[figure not shown]
5. Study visit 2:

- Days 1 & 2: At-home diary.
- Day 3: Test session and diary
- Days 4 & 5: At-home diary

Bladder Function	
Did you have any leakage or incontinence?	
• None• Some• A lot
Did you need to use the bathroom at night?	
• No• Once• Multiple times
How did your bladder function compare to the prior day?	
• Worse• The same• Better
Bowel Function	
Did you have a regular bowel event?	
• No• Almost, or with help• Yes
Did you have fecal incontinence?	
• No• Once• Multiple times
How did your bowel function compare to the prior day?	
• Worse• The same• Better
Sexual Function	
Were you sexually active with a partner or by yourself?	
• No• Self• Partner
If active, did you feel genital arousal or lubrication?	
• No• Some• Yes
If active, did you have an orgasm?	
• No• Yes
Changes in Pelvic Sensation	
Did you experience any atypical sensations from your pelvic region?	
• No• Yes
If yes, please elaborate:	

Figure 3. Pelvic function daily diary questions

Figure 4 provides a visual summary of the timeline for each study participant.

3. Study Statistics and Data Analysis Plan

3.1 Sample size

The target population size (N=40) is based on intended recruitment of 40 women; 10 normal women (e.g. without SCI nor FSD), 10 non-SCI women with FSD, and 20 women with SCI. Efforts will be made to recruit equal numbers between AIS A SCI and AIS B-C SCI participants, but it may be challenging to get exactly 10 in each SCI group. The AIS A SCI and AIS B-C SCI is based on the International Standards for Neurological Classification of Spinal Cord Injury. AIS A SCI refers to complete, no sensory or motor function SCI, while AIS B-C SCI refers to incomplete SCI (e.g. sensory but not motor function is preserved). This is a pilot study with no comparable studies for identifying an effect size and performing a power analysis. If we determine that a larger population size is needed for any participant groups, based on preliminary data analyses, then the target group size will be increased.

3.2 Data Analysis plan

VPA will undergo optimization, filtration, and a spectral analysis as in [11], [12], [15]. The change in VPA from the average baseline value will be determined for each stimulation at four-minute intervals, during which stimulation is paused for ten seconds. Although VPA will be recorded continuously, the genital nerve stimulation may cause a motion artifact and so equal pauses in stimuli will be used in each interval for both stimulation approaches. We may eliminate this pause if data analysis indicates that there are no artifacts or that filtration and spectral analysis eliminates artifacts. Similar calculations may be done for the heart rate and blood pressure. An ANOVA will be performed to determine whether participant type, stimulation location, and stimulation interval (i.e. timing within stimulation duration) has an effect on VPA. Wilcoxon signed rank tests will be used to test for differences within the groups. Similarly, changes in cardiovascular parameters will be assessed, to see if general autonomic responses are triggered with either stimulation location or patient group. We will also look for correlations between the pre-session survey scores (e.g. FSFI total score), patient demographics (e.g. age,

BMI), and changes in items (e.g. decrease in incontinence events) with the maximal VPA responses with a regression analysis.

4. Study Recruitment

This study addresses a potentially sensitive topic. During the recruitment and consenting processes, all study activities will be carefully explained with particular attention to matters of privacy and confidentiality. Many women with spinal cord injury (SCI) have had negative healthcare experiences with respect to reproductive health. Alternatively, grateful patients can feel compelled to participate out of a sense of loyalty. As such, for recruitment and consenting processes, we will emphasize that participation is entirely voluntary, and refusal or withdrawal will have no effect on any care they receive.

SCI participants will primarily be recruited through direct interactions with clinicians on the study team, Drs. [name] and [name], in their clinical practice. We will also seek referrals from clinical colleagues who work with SCI women. Additionally, colleagues of [name] and [name] may distribute or post the study flyer in their urogynecology or SCI clinics. Women with female sexual dysfunction (FSD) may also be recruited from urogynecology or sexual health clinics run by a member of the study team or a colleague. If this occurs, these colleagues will have a general understanding of the study and will refer any patient questions to study investigators or the study coordinator. We will place flyers in relevant Physical Medicine & Rehabilitation, Urology, and Obstetrics & Gynecology clinics. We will also advertise the study on an online University of Michigan health research portal (umhealthresearch.org). Additionally, we will place flyers at several clinics outside of the UM healthcare system in Southeast Michigan, specifically, Detroit Medical Center/Wayne State, PM& R/Novi Rehab Institute of Michigan) and John D. Dingell VA Medical Center. Furthermore, this study will recruit via social media platforms (Facebook and Instagram). The study will be advertised via these social media platforms and direct interested people to the umhealthresearch.org website.

Non-SCI participants will be primarily recruited through the online health portal and we will place flyers in Obstetrics & Gynecology clinics, particularly [name] clinics.

5. Study Population

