1.4 Primary Outcomes

The primary outcome measure in this study is the maximum change in VPA from the average baseline value for each stimulation location across each stimulation participant group. To determine if participant type, stimulation location, and stimulation interval (i.e. timing within stimulation duration) has an effect on VPA, an ANOVA will be performed.

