As shown in Figure 4, during the testing period participants will first view a 5-minute neutral film depicting nature scenes to allow blood flow levels to stabilize. This will be followed by a 10-minute period while the subject watches an erotic film clip for assessment of arousal responses without electrical stimulation. The erotic film clip depicts sexually explicit material of two consenting adults engaging in sexual activities including manual and oral stimulation of breasts and genitals as well as penile-vaginal intercourse depending on the film chosen. A 10-minute clip of the same neutral film will follow, to allow blood flow levels to return to baseline. Five minutes into this film, electrical stimulation will be resumed at the previously determined amplitude. Finally, the subject will view another 10-minute erotic film clip depicting similar sexually explicit material as the first while electrical stimulation remains on as the last sequence in the testing.

At the beginning of the VPA recording sequence, in between each video transition, and at the end of the VPA recording sequence (a total of 5 times), participants will view a 15-30-second screen prompt asking them to record their agreement with the statement, “I feel sexually aroused (e.g. sexually excited, turned on) right now,” according to a 5-point Likert scale: (1) *strongly disagree*, (2) *disagree*, (3) *neutral*, (4) *agree*, and (5) *strongly agree*. At the end of each session participants will be asked their general opinions of that stimulation session, whether it seemed to elicit any genital arousal responses such as lubrication, warmth, tingling, or any

sensations they would characterize as pleasurable, and whether they would consider further use of it.

At the second study day, stimulation using the same steps will be performed at the other location.

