15.4 Frequency and total duration of use for an individual subject

The TENS device will be used once per subject, for 20 minutes of total stimulation during the test session.

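### The ANOVA factor for timing within stimulation is confounded with the change from neutral to erotic film, so its effect cannot be attributed to stimulation timing

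*Combined protocol and SAP*

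**What the plan says.** Section 2.2 sets the order of a session. First, "participants will first view a 5-minute neutral film depicting nature scenes to allow blood flow levels to stabilize". Next comes a "10-minute period while the subject watches an erotic film clip for assessment of arousal responses without electrical stimulation". Then: "A 10-minute clip of the same neutral film will follow, to allow blood flow levels to return to baseline". Stimulation begins partway through that second neutral film: "Five minutes into this film, electrical stimulation will be resumed at the previously determined amplitude". It stays on through a final 10-minute erotic clip. The second visit repeats the same steps at the other stimulation site.

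Section 3.2 says that VPA change, measured against a baseline average, "will be determined for each stimulation at four-minute intervals, during which stimulation is paused for ten seconds". The pauses are there because genital stimulation may cause motion artifact, and they may be dropped if the data show no need for them. The ANOVA is to show whether "participant type, stimulation location, and stimulation interval (i.e. timing within stimulation duration) has an effect on VPA"; section 1.4 puts the same factor beside the primary outcome: "stimulation interval (i.e. timing within stimulation duration) has an effect on VPA, an ANOVA will be performed". Neither section mentions film type, uses the unstimulated erotic film as a comparator, or defines the average baseline value.

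Section 15.4 gives a duration: "The TENS device will be used once per subject, for 20 minutes of total stimulation during the test session".

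**The concern.** The protocol defines the interval factor as timing within stimulation, so a reader of the results would take an interval effect to mean that the response to stimulation builds up or fades. But the film also changes during stimulation, always at the same point. The erotic clip is included because it may enhance arousal, so the protocol itself expects film to move VPA. With no film term and no film-matched control, the ANOVA cannot tell the two explanations apart, and a response to the film would be reported as a property of the stimulation. Section 1.2 asks whether stimulation causes a short-term change in vaginal blood flow, so this attribution matters.

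**Working it through.** **Inputs.** Film lengths and stimulation onset come from the text of section 2.2 (Figure 4 is not shown in the copy reviewed). The four-minute interval and ten-second pause come from section 3.2, and the 20 minutes from section 15.4. The 15–30 second prompts are ignored at first.

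**Timeline in session minutes.** 0–5 neutral, off; 5–15 erotic, off; 15–20 neutral, off; 20–25 neutral, on; 25–35 erotic, on.

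**The stated duration is not reproduced.** Stimulation per session = (10 − 5) neutral + 10 erotic = 15 minutes, or 2 × 15 = 30 over two visits. Neither is 20. Twenty minutes would follow if stimulation covered the whole second neutral film (10 + 10), which section 2.2 does not say.

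**Reading A: VPA averaged over each interval.** 15 / 4 = 3.75 intervals.

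| Session minutes | Neutral (min) | Erotic (min) | Erotic share |
|---|---|---|---|
| 20–24 | 4 | 0 | 0% |
| 24–28 | 1 | 3 | 3/4 = 75% |
| 28–32 | 0 | 4 | 100% |
| 32–35 | 0 | 3 | 100% |

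Suppose the film raises VPA by a constant R, and stimulation and timing do nothing. The interval means are then 0, 0.75R, R and R: a rising profile produced by film alone.

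**Reading B: VPA read only in the pauses.** If the pauses fall at the four-minute marks (minutes 24, 28 and 32; an assumption, since their placement is not stated), the readings are neutral, erotic, erotic. No reading is mixed, but film alone gives 0, R, R. Placement hardly matters: any pause within 20–24 is under neutral film and any within 28–32 is under erotic film.

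**Variants.**
- Prompt at the film change (0.25–0.5 min): the second interval holds 2.75 to 2.5 minutes of erotic film (69% to 62%) and the last is 3.25 to 3.5 minutes long.
- Pause added to each four minutes: 15 / (4 + 10/60) = 3.6 intervals, with erotic shares of 0%, 80%, 100% and 100%.
- 20 minutes as 10 neutral + 10 erotic: 20 / 4 = 5 whole intervals, with erotic shares of 0%, 0%, 50%, 100% and 100%. One interval is still mixed.

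Under every variant the early intervals are neutral and the late ones erotic.

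**Can the recorded data separate the two?** Largely. Minutes 0–15 (off) and 20–35 (on) each consist of 5 minutes of neutral then 10 minutes of erotic film. Write V for mean VPA in a window and let the film response have the same shape in both runs. Then

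T = [V(30–35) − V(25–30)] − [V(10–15) − V(5–10)]

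has expectation zero if film alone acts, even when the film response builds up within the clip.

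**The case against.** A reader might infer that the interval factor measures film and carries no timing information. That goes too far. Intervals 28–32 and 32–35 lie wholly within the erotic film, so their contrast does reflect time under stimulation, though mixed with any build-up of the film response and, if averaged, with a shorter last interval. What fails is attribution of the overall interval effect.

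A reader might also infer that the four-minute grid necessarily straddles the film change, or that it would be sound with 20 minutes of stimulation. The straddle and the short last interval arise only if VPA is averaged, and section 3.2 also allows reading in the pauses. With 20 minutes the grid divides evenly but still leaves a mixed interval. Confounding with film remains in all these cases.

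It is tempting to quote a false-positive rate. The documents give neither a film response nor a standard deviation, and the plan names no pairwise interval test, so any rate would only restate an assumed R. One R for all groups would also be hard to defend: section 1.1 says spinal cord injury interrupts the link between central sexual circuits and genital arousal, and section 3.1 aims for about half of the 20 injured women to have complete injuries.

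Finally, the three aims compare stimulation sites, the primary outcome is a maximum change, and this is a pilot without a power calculation. That limits the consequence: both visits use the same film sequence, so the genital-versus-tibial contrast is not biased by this. Yet interval is one of three named factors in the ANOVA tied to the primary outcome, and its stated meaning is not supported.

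**Conclusion.** The point holds. On the section 2.2 timeline the film changes at stimulation minute 5 of 15, and the ANOVA has neither a film term nor a film-matched unstimulated comparison. The interval main effect is therefore confounded with film and cannot be attributed to stimulation timing. This holds whether VPA is averaged or read in the pauses, and with 15 or 20 minutes of stimulation. A film response R would appear as 0, 0.75R, R, R (averaged) or 0, R, R (pause readings); R is unknown from the documents. The conclusion rests on the text of section 2.2 and on the protocol's own expectation that erotic film can raise arousal. It does not extend to the comparison of stimulation sites. The duration conflict between sections 2.2 and 15.4 is a separate inconsistency.

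**What to change.** In section 3.2:

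- Replace the four-minute analysis intervals with film-aligned windows 20–25, 25–30 and 30–35, and compare each with its unstimulated counterpart 0–5, 5–10 and 10–15.
- Enter film and stimulation (off/on) as within-woman factors, alongside location and participant type.
- Test timing by T above. A contrast of 20–25 with later windows, even against its unstimulated counterpart, still mixes timing with any film-by-stimulation interaction and should not be labelled timing.
- State whether VPA is averaged over the window or read in the pauses. Pauses at minutes 24, 28 and 32 fall one per window, with matched unstimulated readings at minutes 4, 8 and 12, so the delivered stimulation need not change.
- Define the average baseline value so that minutes 0–5 do not serve as both baseline and comparator; otherwise the change in that window is zero by construction.

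Separately, reconcile sections 2.2 and 15.4 on stimulation duration. If the reconciled timeline differs from the one used here, redraw the windows at its film changes.

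The cost is a few sentences of analysis text and no new data. There is one time point fewer than with four averaged intervals, and none fewer than with three pause readings. One limitation must be reported: the stimulated run always comes second, so off/on remains confounded with order, carry-over and habituation. The matched windows are not fully alike either: 0–5 is the initial stabilisation period, 20–25 follows an erotic clip and five minutes of recovery, and the second erotic clip is similar to the first, not identical.

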women and non-neurogenic women with FSD will also provide information about the underlying neural circuitry, based on whether either stimulation approach has better efficacy in spinal intact or damaged participants. While genital nerve stimulation is generally successful at improving bladder function in individuals with SCI, tibial nerve stimulation has had mixed results. These findings by other researchers suggest potential outcomes for our different study groups.

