1.2 Objective

The overall purpose of this research is to improve sexual function in women with sexual dysfunction. The goal of this study is to see if either of two nerve stimulation interventions cause a short-term change in vaginal blood flow. The effect of this intervention will be compared between women who have neurogenic (spinal cord injury) or non-neurogenic dysfunction and healthy women, to reveal mechanisms underlying neural control over vaginal blood flow.

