1.3 Specific Aims

The aims of this study are to:

- Aim 1: Compare the effect of skin-surface genital nerve stimulation and tibial nerve stimulation on vaginal blood flow in women with spinal cord injury caused neurogenic sexual dysfunction.
- Aim 2: Compare the effect of skin-surface genital nerve stimulation and tibial nerve stimulation on vaginal blood flow in women with non-neurogenic female sexual dysfunction.
- Aim 3: Compare the effect of skin-surface genital nerve stimulation and tibial nerve stimulation on vaginal blood flow in neurologically-intact women without sexual dysfunction.

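### The primary ANOVA names no participant or session error term and no type-by-location interaction for paired two-visit data, and its response variable and the levels of participant type are not fixed

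*Combined protocol and SAP*

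**What the plan says.** Section 3.2 states: "An ANOVA will be performed to determine whether participant type, stimulation location, and stimulation interval" affect VPA. Section 1.4 lists the same three factors. Neither section names a participant, session, visit or interaction term, and no other available section does.

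Section 2.2 makes the data paired. Each woman attends twice, one to five months apart. One location is chosen at random for the first visit and the other is used at the second.

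The response is described in two ways. Section 1.4: "The primary outcome measure in this study is the maximum change in VPA from the average baseline value for each stimulation location", which is one value per visit. Section 3.2: "The change in VPA from the average baseline value will be determined for each stimulation at four-minute intervals", which is several values per visit.

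The aims are within-group. Aim 2, for example, is to "Compare the effect of skin-surface genital nerve stimulation and tibial nerve stimulation on vaginal blood flow in women with non-neurogenic female sexual dysfunction". The objective in section 1.2 is between-group: "The effect of this intervention will be compared between women who have neurogenic (spinal cord injury) or non-neurogenic dysfunction and healthy women". Section 1.1 says that the groups will inform about neural circuitry "based on whether either stimulation approach has better efficacy in spinal intact or damaged participants".

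Section 3.2 adds: "Wilcoxon signed rank tests will be used to test for differences within the groups". It does not say which differences.

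Sections 1.2, 1.3, 5.1 and 5.2 use three participant types. Section 3.1 counts 20 women with SCI but plans an AIS A and an AIS B-C group and says "it may be challenging to get exactly 10 in each SCI group".

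**The concern.** Values from the same woman are likely to be correlated, and values from the same session more so. An ANOVA with one pooled residual treats all of them as independent. Participant type varies only between women, so it should be judged against variation between women. The pooled residual mixes that with variation within women and claims far more degrees of freedom than 40 women supply. The between-group comparison in section 1.2 is then prone to false positives.

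Location and type-by-location are within-woman contrasts, and for them the error can go either way. The section 1.1 question, whether the better location depends on cord status, is an interaction, and three main effects cannot answer it.

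The model is also not fully defined. A single maximum per visit has no interval dimension, so interval cannot be a factor for the section 1.4 outcome. Section 3.1 lets preliminary analyses enlarge groups, so a misleading analysis could also affect recruitment.

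**Working it through.** **Inputs from the documents.** Groups of 10, 10 and 20 (10 + 10 + 20 = 40, agreeing with section 3.1); two locations per woman; four-minute intervals. Stimulation time by the section 2.2 sequence is 5 + 10 = 15 minutes, and 15/4 gives K = 3 full intervals. Section 15.4 says 20 minutes, and 20/4 gives K = 5; it also says the device is used once per subject, against two visits. No alpha, power, effect size, variance or correlation is stated, so there is no sample-size calculation to reproduce.

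**Assumptions.** Nominal 5%; normal errors; total variance 1, split into participant share a, session share s and residual share e.

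**Expected mean squares with no true effects.**
- Type: 2Ka + Ks + e
- Location, and type-by-location: Ks + e
- Pooled residual of the literal model: close to a + s + e = 1

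Type is therefore too liberal whenever (2K − 1)a + (K − 1)s > 0. Location and the interaction are too liberal roughly when (K − 1)s > a, and too strict when it is smaller.

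Residual degrees of freedom in the literal model are 80 − 4 = 76, 240 − 6 = 234 and 400 − 8 = 392 for K = 1, 3 and 5. Three types among 40 women leave 40 − 3 = 37.

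**Simulated false-positive rates, three types, listed factors only.** In the interaction column the term is added without a participant or session term. Rates are rounded; separate runs agree within about two percentage points.

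| Data | Shares a/s/e | Mean square: type; location | Type | Location | Interaction |
|---|---|---|---|---|---|
| K = 3 | 0.2/0/0.8 to 0.7/0/0.3 | 2.0 to 4.5; 0.8 to 0.3 | 22 to 54% | too strict | too strict |
| K = 5 | 0.2/0/0.8 to 0.7/0/0.3 | 2.8 to 7.3; 0.8 to 0.3 | 35 to 69% | too strict | too strict |
| K = 3 | 0.3/0.4/0.3 | 3.3; 1.5 | 41% | 12% | 15% |
| K = 5 | 0.3/0.4/0.3 | 5.3; 2.3 | 57% | 21% | 28% |
| K = 3 | 0/0.7/0.3 | 2.4; 2.4 | 28% | too liberal | too liberal |
| K = 5 | 0/0.7/0.3 | 3.8; 3.8 | 47% | too liberal | too liberal |
| One maximum per visit (interval omitted) | correlation 0.2 to 0.7 | 1.2 to 1.7; 0.8 to 0.3 | 9 to 18% | 3% down to 0.1% | 2% down to under 0.1% |

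The rows with s = 0 assume that intervals minutes apart in one session are no more alike than sessions months apart. The 0/0.7/0.3 rows show that zero correlation between visits does not restore 5% when intervals are analysed. Only with one value per visit does zero correlation do so.

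**Lost power, one maximum per visit, correlation 0.5.** For a location difference of 0.3 SD, power is 20% against 45% for the paired test; for 0.5 SD it is 65% against 87%.

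**Correct error term.** Testing type on participant means, and location and the interaction on within-woman differences, returns about 5% in every setting tried.

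**If SCI is split (four types of 10).** With s = 0 and correlations 0.2 to 0.7, type is 9 to 20% (one value), 28 to 64% (K = 3) and 43 to 80% (K = 5).

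**The case against.** The strongest reply is that the plan is underspecified rather than wrong. An ANOVA with a within-session factor may well be meant as repeated-measures, and the study is a pilot with no stated alpha or power. That stands, so every rate above is conditional on a literal reading. But a repeated-measures form would still leave the response, the number of types, the visit term and the interaction unstated.

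Second, all three aims compare locations within a group, and a signed-rank test is paired. This also stands. A reader might infer that Aims 1 to 3 have no valid test; the documents do not support that. What the Wilcoxon tests lack is a named contrast, an adjustment for visit, and any comparison between groups.

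Third, a reader might take section 1.2 to require the interaction. On a change-from-baseline response it can equally mean the type main effect, or both. The interaction rests on section 1.1, which is background.

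Fourth, a reader might infer that the location test gives too many false positives. It does so only with interval-level data and enough session variance; otherwise it is too strict.

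Finally, the 80% figure combines four types, five intervals and correlation 0.7. Most sections use three types, and the section 15.4 basis for five intervals is itself inconsistent with two visits. It is an extreme, not an expectation. Nor is the lack of stated balance in visit order a bias: order is randomised, and any imbalance is by chance.

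**Conclusion.** The point holds as a gap in specification that should be closed before analysis. It is not evidence that an invalid analysis will be run, and the two-visit design itself is sound.

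If the three listed factors were used as they stand, the test of participant type would be too liberal under every variance split examined: about 9 to 18% with one maximum per visit and roughly 22 to 69% with interval-level data, against a nominal 5%. The exact size rests on assumed variance shares. The direction for type needs only some positive participant variance or, with interval-level data, some session variance. For location and the interaction the direction depends on the response chosen and on session variance, so no single direction can be claimed.

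The conflict between sections 1.4 and 3.2 over the response, and the open choice of three or four types, do not depend on any assumption. The available text lacks Figure 4 and some removed pages, so the finding is limited to what can be read.

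**What to change.** 1. State whether the response is one maximum per visit (then drop interval) or interval-level change, and whether participant type has three or four levels.
2. Name a linear mixed model, or the equivalent repeated-measures ANOVA, with a random participant effect, plus session within participant for interval-level data. Fixed effects: type, location, type-by-location, visit and, if used, interval. Use a small-sample degrees-of-freedom method, for example Kenward-Roger.
3. Report the location effect within each group, and the interaction, with 95% confidence intervals as pilot estimates.
4. State that the Wilcoxon tests compare genital with tibial stimulation within each group, as support.
5. Reconcile the stimulation time and number of uses in sections 2.2 and 15.4, because they set the number of intervals.
6. Optional and secondary: assign the order for women not yet randomised in small blocks within type.

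The cost is one paragraph of wording, one degree of freedom for visit, and two (three types) or three (four types) for the interaction. No patients or procedures are added. Precision stays low. With one value per visit, equal variance across groups and correlation 0.2 to 0.7, the 95% half-width for location is t × √(2(1 − r)) × √(1/n), with t on 36 degrees of freedom: 0.81 to 0.50 SD for n = 10 and 0.57 to 0.35 SD for n = 20.
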